12.6.7 Overall Response Assessment

The overall response assessment takes into account response in both target and non-target lesions, the appearance of new lesions and normalization of markers (where applicable), according to the criteria described in the table below. The overall response assessment is shown in the last column, and depends on the assessments of target, non-target, marker and new lesions in the preceding columns.

Target Lesions	Non-target Lesions	Markers	New Lesions	Overall Response
CR	CR	Normal	No	CR
CR	IR/SD	Normal	No	PR
CR	CR, IR/SD	Abnormal	No	PR
PR	CR, IR/SD	Any	No	PR
SD	CR, IR/SD	Any	No	SD
PD	Any	Any	Yes or No	PD
Any	PD	Any	Yes or No	PD
Any	Any	Any	Yes	PD

Each patient will be classified according to his “best response” for the purposes of analysis of treatment effect. Best response is determined as outlined in [Section 12.8](#) from a sequence of overall response assessments.

12.7 Best Response

12.7.1 Evaluation of Best Overall Response

The best overall response is the best response recorded from the start of the treatment until disease progression/recurrence (taking as reference for progressive disease the smallest measurements recorded since the treatment started). The patient's best response assignment will depend on the achievement of both measurement and confirmation criteria.

Table 1. Sequences of overall response assessments with corresponding best response.

1 st Assessment	2 nd Assessment	Best Response
Progression		Progressive disease
Stable, PR, CR	Progression	Progressive disease
Stable	Stable	Stable
Stable	PR, CR	Stable
Stable	Not done	Not RECIST classifiable
PR	PR	PR
PR	CR	PR
PR, CR	Not done	Not RECIST classifiable
CR	CR	CR

12.7.2 Duration of Response

Duration of overall response: The duration of overall response is measured from the time measurement criteria are met for CR or PR (whichever is first recorded) until the first date that recurrent or progressive disease is objectively documented (taking as reference for progressive disease the smallest measurements recorded since the treatment started).

The duration of overall CR is measured from the time measurement criteria are first met for CR until the first date that progressive disease is objectively documented.

Duration of stable disease: Stable disease is measured from the start of the treatment until the criteria for progression are met, taking as reference the smallest measurements recorded since the treatment started, including the baseline measurements.

13.0 ADVERSE EVENT REPORTING REQUIREMENTS

Adverse event data collection and reporting which are required as part of every clinical trial, are done to ensure the safety of patients enrolled in the studies as well as those who will enroll in future studies using similar agents. Adverse events are reported in a routine manner at scheduled times during a trial. (Please follow directions for routine reporting provided in the Case Report Forms for this protocol). Additionally, certain adverse events must be reported in an expedited manner to allow for optimal monitoring of patient safety and care. The following sections provide information about

expedited reporting.

Reporting requirements may include the following considerations: 1) whether the patient has received an investigational or commercial agent; 2) whether the adverse event is considered serious; 3) the grade (severity); and 4) whether or not hospitalization or prolongation of hospitalization was associated with the event.

An investigational agent is a protocol drug administered under an Investigational New Drug Application (IND). In some instances, the investigational agent may be available commercially, but is actually being tested for indications not included in the approved package label.

Commercial agents are those agents not provided under an IND but obtained instead from a commercial source. The NCI, rather than a commercial distributor, may on some occasions distribute commercial agents for a trial.

13.1 Steps to Determine If an Adverse Event Is To Be Reported In an Expedited Manner

Step 1: Identify the type of adverse event using the NCI CTCAE version 5.0. The descriptions and grading scales found in the CTCAE version 5.0 will be used for AE reporting. All appropriate treatment areas should have access to a copy of the CTCAE version 5.0. A copy of the CTCAE version 5.0 can be downloaded from the CTEP website (http://ctep.cancer.gov/protocolDevelopment/electronic_applications/ctc.htm).

Step 2: Grade the adverse event using the NCI CTCAE version 5.0.

Step 3: Review Table A in this section to determine if:

- the adverse event is considered serious;
- there are any protocol-specific requirements for expedited reporting of specific adverse events that require special monitoring; and/or
- there are any protocol-specific exceptions to the reporting requirements.

Note: This includes all events that occur within 30 days of the last dose of protocol treatment. Any event that occurs more than 30 days after the last dose of treatment and is attributed (possibly, probably, or definitely) to the agent(s) must also be reported according to the instructions in the table below. Attribution categories are as follows: Unrelated, Unlikely, Possible, Probable, and Definite.

Table A: Phase 1 and Early Phase 2 Studies: Expedited Reporting Requirements for Adverse Events that Occur on Studies under an IND/IDE within 30 Days of the Last Administration of the Investigational Agent/Intervention^{1,2}

FDA REPORTING REQUIREMENTS FOR SERIOUS ADVERSE EVENTS (21 CFR Part 312)

NOTE: Investigators **MUST** immediately report to the sponsor **ANY** Serious Adverse Events, whether or not they are considered related to the investigational agent(s)/intervention (21 CFR 312.64)

An adverse event is considered serious if it results in **ANY** of the following outcomes:

- 1) Death
- 2) A life-threatening adverse event
- 3) An adverse event that results in inpatient hospitalization or prolongation of existing hospitalization for ≥ 24 hours
- 4) A persistent or significant incapacity or substantial disruption of the ability to conduct normal life functions
- 5) A congenital anomaly/birth defect.
- 6) Important Medical Events (IME) that may not result in death, be life threatening, or require hospitalization may be considered serious when, based upon medical judgment, they may jeopardize the patient or subject and may require medical or surgical intervention to prevent one of the outcomes listed in this definition. (FDA, 21 CFR 312.32; ICH E2A and ICH E6).

ALL SERIOUS adverse events that meet the above criteria **MUST** be immediately reported via CTEP-AERS within the timeframes detailed in the table below.

Hospitalization	Grade 1 and Grade 2 Timeframes	Grade 3-5 Timeframes
Resulting in Hospitalization ≥ 24 hrs	7 Calendar Days	24-Hour 5 Calendar Days
Not resulting in Hospitalization ≥ 24 hrs	Not required	

NOTE: Protocol-specific exceptions to expedited reporting of serious adverse events are found below under the section entitled “Additional Instructions or Exceptions.”

Expedited AE reporting timelines are defined as:

- “24-Hour; 5 Calendar Days” - The AE must initially be reported via CTEP-AERS within 24 hours of learning of the AE, followed by a complete expedited report within 5 calendar days of the initial 24-hour report.
- “7 Calendar Days” - A complete expedited report on the AE must be submitted within 7 calendar days of learning of the AE.

¹Serious adverse events that occur more than 30 days after the last administration of investigational agent/intervention and have an attribution of possible, probable, or definite require reporting as follows:

Expedited 24-hour notification followed by complete report within 5 calendar days for:

- All Grade 3, 4, and Grade 5 AEs

Expedited 7 calendar day reports for:

- Grade 2 AEs resulting in hospitalization or prolongation of hospitalization

² For studies using PET or SPECT IND agents, the AE reporting period is limited to 10 radioactive half-lives, rounded UP to the nearest whole day, after the agent/intervention was last administered. Footnote “1” above applies after this reporting period.

Effective Date: May 5, 2011

- Any medical event equivalent to CTCAE version 5.0 grade 3, 4, or 5 that precipitates hospitalization (or prolongation of existing hospitalization) must be reported regardless of attribution and designation as expected or unexpected with the exception of any events identified as protocol-specific expedited adverse event reporting exclusions.
- Any event that results in persistent or significant disabilities/incapacities, congenital anomalies, or birth defects must be reported via CTEP-AERS if the event occurs following treatment with an agent under a CTEP IND.
- Use the NCI protocol number and the protocol-specific patient ID provided during trial registration on all reports.

Additional Instructions or Exceptions to CTEP-AERS Expedited Reporting Requirements for Phase 1 Trials Utilizing an Agent under a CTEP-IND or Non-CTEP IND:

- Any death that occurs more than 30 days after the last dose of treatment with an investigational agent which can be attributed (possibly, probably, or definitely) to the agent and is not clearly due to progressive disease must be reported via CTEP-AERS for an agent under a CTEP or non-CTEP IND agent per the timelines outlined in the table above.
- Myelosuppression, (Grade 1 through Grade 4 adverse events as defined in the table below), does not require expedited reporting, unless it is associated with hospitalization.

Category	Adverse Events
INVESTIGATIONS	Platelet count decreased
INVESTIGATIONS	White blood cell decreased
INVESTIGATIONS	Neutrophil count decreased
INVESTIGATIONS	Lymphocyte count decreased
BLOOD/LYMPHATICS DISORDERS	Anemia

- Grade 1 and 2 adverse events listed in the table below do **not** require expedited reporting via CTEP-AERS:

Category	Adverse Events
GASTROINTESTINAL DISORDERS	Nausea
GASTROINTESTINAL DISORDERS	Vomiting
GASTROINTESTINAL DISORDERS	Constipation
GENERAL DISORDERS AND ADMINISTRATION SITE CONDITIONS	Fatigue
INFECTIONS AND INFESTATIONS	Mucosal inflammation
INFECTIONS AND INFESTATIONS	Thrush
INFECTIONS AND INFESTATIONS	Infection
INVESTIGATIONS	Weight loss
INVESTIGATIONS	Aspartate aminotransferase increased
METABOLISM AND NUTRITION DISORDERS	Hypokalemia
METABOLISM AND NUTRITION DISORDERS	Hypophosphatemia

METABOLISM AND NUTRITION DISORDERS	Hypertriglyceridemia
RESPIRATORY, THORACIC AND MEDIASTINAL DISORDERS	Dyspnea
SKIN AND SUBCUTANEOUS TISSUE DISORDERS	Rash/desquamation

As referenced in the CTEP Adverse Events Reporting Requirements, an AE that resolves and then recurs during a subsequent cycle does not require CTEP-AERS reporting unless (1) the Grade increases; or (2) hospitalization is associated with the recurring AE.

13.2 When to Report an Event in an Expedited Manner

- Some adverse events require notification **within 24 hours** (refer to [Table A](#)) to NCI via the web at <http://ctep.cancer.gov> (email the ADVL1514 COG Study Assigned Research Coordinator within 24 hours of becoming aware of the event if the CTEP-AERS 24-Hour Notification web-based application is unavailable) and by telephone call to the Study Chair. Once internet connectivity is restored, a 24-hour notification phoned in must be entered electronically into CTEP-AERS by the original submitter at the site.
- When the adverse event requires expedited reporting, submit the report **within 5 or 7 calendar days** of learning of the event (refer to [Table A](#)).
- Expedited AE reporting for this study must only use CTEP-AERS (Adverse Event Expedited Reporting System), accessed via the CTEP home page <https://eapps-ctep.nci.nih.gov/ctepaers>.

13.3 Expedited Reporting Methods

13.3.1 CTEP-AERS Reporting

To report adverse events in an expedited fashion use the NCI's Adverse Event Expedited Reporting System (CTEP-AERS) that can be found at <http://ctep.cancer.gov>.

A CTEP-AERS report must be submitted electronically via the CTEP-AERS Web-based application located at <https://ctepcore.nci.nih.gov/ctepaers>. If prompted to enter a sponsor email address, please type in: [contact].

Email supporting documentation to the ADVL1514 COG Study Assigned Research Coordinator. **ALWAYS include the ticket number on all faxed and emailed documents.**

13.4 Definition of Onset and Resolution of Adverse Events

Note: These guidelines below are for reporting adverse events on the COG case report forms and do not alter the guidelines for CTEP-AERS reporting.

- 13.4.1** If an adverse event occurs more than once in a course (cycle) of therapy only the most severe grade of the event should be reported.
- 13.4.2** If an adverse event progresses through several grades during one course of therapy, only the most severe grade should be reported.
- 13.4.3** The duration of the AE is defined as the duration of the highest (most severe) grade of the Adverse Effects.
- 13.4.4** The resolution date of the AE is defined as the date at which the AE returns to baseline or less than or equal to Grade 1, whichever level is higher (note that the resolution date may therefore be different from the date at which the grade of the AE decreased from its highest grade). If the AE does not return to baseline the resolution date should be recorded as "ongoing."
- 13.4.5** An adverse event that persists from one course to another should only be reported once unless the grade becomes more severe in a subsequent course. An adverse event which resolves and then recurs during a different course, must be reported each course it recurs.

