5.5.1 Non-hematological dose-limiting toxicity

5.5.1.1 Any Grade 3 or greater non-hematological toxicity attributable to the protocol therapy with the specific exclusion of:

- Grade 3 nausea and vomiting < 3 days duration
- Grade 3 liver enzyme elevation, including ALT/AST/GGT, that returns to Grade ≤ 1 or baseline prior to the time for the next treatment cycle.
Note: For the purposes of this study the ULN for ALT is defined as 45 U/L and the ULN for AST is defined as 50 U/L, regardless of baseline. See [Appendix XV](#) for values that represent thresholds between CTCAE grades for ALT, AST, GGT and bilirubin.
- Grade 3 fever
- Grade 3 infection
- Grade 3 hypophosphatemia, hypokalemia, hypocalcemia or hypomagnesemia responsive to supplementation.
- Grade 3 or 4 hypertriglyceridemia that returns to Grade ≤ 2 prior to the start of the next treatment cycle. The severity (grade) of hypertriglyceridemia is based upon fasting levels. If Grade 3 or 4 triglycerides are detected when routine (non-fasting) laboratory studies are performed, the test should be repeated within 3 days in the fasting state to permit accurate grading (see [Section 6.4](#)).
- Grade 3 hyperglycemia that returns to a fasting glucose value ≤ 250 mg/dL or a fasting glucose of value ≤ 13.9 mmol/L (with or without the use of insulin or oral diabetic agents) prior to the start of the next treatment cycle. Medical management of hyperglycemia should be based on fasting levels. If routine (non-fasting) laboratory studies are performed and indicate the potential for intervention, the test should be repeated within 3 days in the fasting state to permit accurate medical management and grading (see [Section 6.6](#)).
- Grade 3 or 4 hypercholesterolemia that returns to \leq Grade 2 after initiation of lipid lowering medication prior to the next treatment cycle. The severity (grade) of hypercholesterolemia is based upon fasting levels. If Grade 3 or 4 hypercholesterolemia is detected when routine (non-fasting) laboratory studies are performed, the test should be repeated within 3 days in the fasting state to permit accurate grading (see [Section 6.5](#)).

5.5.1.2 Non-hematological toxicity that causes a delay of > 21 days between treatment cycles.

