10.0 CRITERIA FOR REMOVAL FROM PROTOCOL THERAPY AND OFF STUDY CRITERIA

10.1 Criteria for Removal from Protocol Therapy

- a) Clinical (including physical examination or serum tumor markers) or radiographic evidence of progressive disease (See [Section 12.0](#)).

- b) Adverse Events requiring removal from protocol therapy (See [Section 6.0](#)).
- c) Refusal of protocol therapy by patient/parent/guardian
- d) Non-compliance that in the opinion of the investigator does not allow for ongoing participation.
- e) Completion of 35 cycles of therapy.
- f) Physician determines it is not in the patient's best interest.
- g) Repeated eligibility laboratory studies (CBC with differential, bilirubin, ALT (SGPT) or serum creatinine) are outside the parameters required for eligibility prior to the start of ABI-009 (See [Section 8.1](#)).
- h) Study is terminated by Sponsor.
- i) Pregnancy

Patients who are removed from protocol therapy during cycle 1 should continue to have the required observations in [Section 8.1](#) until the originally planned end of the cycle or until all adverse events have resolved per [Section 13.4.4](#), whichever happens LATER. The only exception is with documentation of the patient's withdrawal of consent. Patients who are removed from protocol therapy in subsequent cycles should have the necessary observations to ensure adequate clinical care.

Patients who are off protocol therapy are to be followed until they meet the criteria for Off Study (see below). Ongoing adverse events, or adverse events that emerge after the patient is removed from protocol therapy, but within 30 days of the last dose of investigational agent, must be followed and reported via RAVE and CTEP-AERS (if applicable). Follow-up data will be required unless consent is withdrawn.

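### Section 13.4.4 treats an event that was absent at baseline and falls to Grade 1 as both resolved and ongoing; on one reading of 13.4.5, a same-grade repeat in Cycle 2 then goes unrecorded

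*Combined protocol and SAP*

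**What the plan says.** Section 13.4 governs adverse event entries on the COG case report forms. Its opening note says that its rules "do not alter the guidelines for CTEP-AERS reporting".

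- **13.4.4, first sentence.** The resolution date is "the date at which the AE returns to baseline or less than or equal to Grade 1, whichever level is higher".
- **13.4.4, last sentence.** "If the AE does not return to baseline the resolution date should be recorded as" ongoing.
- **13.4.5, persisting events.** "An adverse event that persists from one course to another should only be reported once unless the grade becomes more severe in a subsequent course".
- **13.4.5, recurring events.** "An adverse event which resolves and then recurs during a different course, must be reported each course it recurs".

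Section 10.1 also relies on 13.4.4. A patient removed from protocol therapy in Cycle 1 keeps the required observations "until the originally planned end of the cycle or until all adverse events have resolved per" Section 13.4.4, and the later of the two dates applies.

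**The concern.** The first sentence of 13.4.4 sets the threshold at the higher of baseline and Grade 1. The last sentence sets it at baseline. No other section says which governs. Under 13.4.5, whether an earlier event has resolved or is persisting decides how a later episode is handled, so the disagreement can reach the data.

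This design is sensitive to it because Cycle 1 is ABI-009 alone and the combination starts in Cycle 2. Single-agent and combination toxicities are separate primary aims (1.1.2 and 1.1.3). An event first seen in Cycle 1 and repeated in Cycle 2 bears on both aims, and the entry at risk is the combination one. The planned output is a descriptive summary of all toxicities (Section 11.3), which a missing entry would affect directly.

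**Working it through.** The plan gives no figure to reproduce here. The check writes the rules out and follows them through.

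**Step 1. Where the two sentences disagree.** Let b be the baseline grade and g the current grade.

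- First sentence: resolved if g ≤ max(b, 1).
- Last sentence: ongoing if g > b.
- Both apply when b < g ≤ max(b, 1).

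| Baseline b | Current g | First sentence | Last sentence |
|---|---|---|---|
| 0 | 0 | resolved | not ongoing |
| 0 | 1 | resolved | ongoing (conflict) |
| 0 | 2 or more | not resolved | ongoing |
| 1 or more | at or below b | resolved | not ongoing |
| 1 or more | above b | not resolved | ongoing |

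For b ≥ 1, max(b, 1) = b, so the two agree. The only conflict is b = 0, g = 1.

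**Step 2. Consequence under 13.4.5.** Take a Grade 3 event in Cycle 1 that falls to Grade 1 and returns to Grade 3 in Cycle 2. The grade already reported for Cycle 1 is 3, because 13.4.1 and 13.4.2 report the most severe grade in a course.

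| Status before Cycle 2 | Worsening judged against the grade already reported | Worsening judged against the grade carried into Cycle 2 |
|---|---|---|
| Resolved | recorded, as a recurrence | recorded, as a recurrence |
| Ongoing | not recorded (3 is not above 3) | recorded (3 is above 1) |

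The record is lost in one of the four combinations, so two separate readings are both needed.

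**Step 3. An illustration on the protocol's own cut-offs.** The ALT values are hypothetical. Grades are from Appendix XV.

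- Baseline 30 U/L: below the 45 U/L ULN, so Grade 0.
- Cycle 1 peak 300 U/L: within 226 to 900, so Grade 3.
- Before Cycle 2, 120 U/L: above 45 and at most 135, so Grade 1. This also meets the 135 U/L limit in 4.1.8.3. Section 5.5.1.1 excludes from DLT a Grade 3 liver enzyme rise "that returns to Grade ≤ 1 or baseline prior to the time for the next treatment cycle", so the Cycle 1 event is not a DLT.
- Cycle 2, 300 U/L again: Grade 3.

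The first sentence gives two entries, one per cycle. The last sentence, with worsening judged against the reported grade, gives one entry, for Cycle 1.

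**Step 4. Other routes.** Section 13.1 requires no new CTEP-AERS report for an event that resolves and recurs in a later cycle unless the grade rises or hospitalization is associated. Expedited reporting would therefore not reliably capture a same-grade repeat. DLTs do have their own route: suspected DLTs go to the Study Chair within 24 hours (5.4), and the Study Chair enters DLT evaluations in the database (14.4.2).

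**Step 5. Size per lost episode.** One patient divided by the number evaluable at Dose Level -2:

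- 6 patients (initial cohort, 11.3.1): 1/6 = 16.7 percentage points.
- 6 + 6 = 12 (with the PK expansion, 11.3.1): 1/12 = 8.3 points.
- 12 + 6 = 18 (expanded cohort plus PK patients, 11.1.1): 1/18 = 5.6 points.

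**Step 6. Section 10.1.** A cycle is 21 days and the later date applies, so observations run at least to Day 21. The two sentences give different end dates only if a new event is still at Grade 1 after Day 21. Section 10.2 takes a patient off study 30 days after the last dose of the investigational agent. After a Day 8 dose that is Day 8 + 30 = Day 38, which is 38 − 21 = 17 days past the planned cycle end. After a Day 1 dose only, it is Day 31, or 10 days past.

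**The case against.** The strongest reply is that the first sentence is the definition and the last is shorthand for not reaching that level. Read literally, the last sentence would leave the clause on the higher level with no effect for any event absent at baseline. Section 5.5.1.1 uses a similar recovery standard for liver enzymes, which also favours the first sentence. This is probably what was intended, but the text does not say so, and a site following the last sentence as written would not be in error.

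A second reply is that 13.4.5 does not mention the ongoing entry, and that a rise from Grade 1 to Grade 3 within Cycle 2 is ordinarily a worsening. This stands in part. A reader might infer that every event marked ongoing at Grade 1 loses its Cycle 2 repeat. The documents do not support that, because the repeat is lost only if worsening is judged against the grade already reported.

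A third reply is that the separate CRF packet (14.1) may settle the entry. It may, but it is not part of the documents reviewed.

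Two further inferences are tempting and also fail. One is that dose-finding is compromised; the separate DLT route in 5.4 and 14.4.2 answers that. The other is that required observations under 10.1 simply stop at Grade 1. They cannot stop before the originally planned end of the cycle, and off-study status limits any difference after it.

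**Conclusion.** The concern holds in a limited form. Section 13.4.4 conflicts with itself only for an event absent at baseline that has fallen to Grade 1. A same-grade repeat in Cycle 2 can then be missing from the case report form record, and so from the combination toxicity summary, provided the site both marks the event ongoing and measures worsening from the grade already reported.

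The documents do not say how often this would happen. The 17 to 6 percentage points are the weight of one patient in 6 to 18, not an estimate of expected bias. They also assume that the summary uses evaluable patients at Dose Level -2 as its denominator, which the plan does not state. Section 11.2.1 counts a patient as evaluable for adverse events after a single dose, so another denominator is possible. DLT counts and dose decisions need not change. The effect on Section 10.1 is confined to a new event still at Grade 1 after the planned end of Cycle 1. This is a wording defect worth correcting, of minor weight.

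**What to change.** Tie the last sentence of 13.4.4 to the level set in the first, for example: *An event that does not come down to that level (the higher of baseline and Grade 1) has no resolution date and is entered as ongoing.* Section 13.4.5 then gives one answer: an event that reached that level and rises again in a later course is a recurrence and is reported in that course.

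Section 10.1 points to 13.4.4 for the end of required observations after removal in Cycle 1. That cross-reference should be reconciled with the amended wording, and with the 30-day off-study criterion in 10.2, so that sites follow one schedule.

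The cost is one sentence in 13.4.4 and a check of the cross-reference. No tests, visits or patients are added.
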